8.6.1.2 Criteria for the Calculation of an Apparent Terminal Elimination Half-Life

• Number of Data Points

 $_{\odot}$ At least three data points will be included in the regression analysis and preferably should not include C_{max}.

• Goodness of Fit

- When assessing terminal elimination phases, the R² adjusted (Rsq_adj) value will be used as a measure of the goodness of fit of the data points to the determined line.
- An elimination half-life will generally only be calculated if the R² adjusted value of the regression line is greater than or equal to 0.7. Exceptions can be made (e.g. CSF) for exploratory purposes.

• Period of Estimation

- $\circ~$ Time period used for the estimation of apparent terminal elimination half-lives, where possible, will be over at least two half-lives (t_{1/2}_interval ratio).
- $\circ~$ Where t_{1/2}_interval ratio < 2 the robustness of the value(s) may be discussed in the study report.

8.6.1.3 Calculation of AUC

- The minimum requirement for the calculation of AUC will be the inclusion of at least three consecutive concentrations above the lower limit of quantification (LLOQ), with at least one of these concentrations following C_{max} .
- For any partial AUC determination (i.e. AUC over a dosing interval), nominal time will generally be used for the end of the interval. Actual times for partial AUC intervals may be used at the discretion of the Pharmacokineticist.
- AUC_{0- ∞} values where the percentage extrapolation is less than 20% will be reported. AUC_{0- ∞} values where the percentage extrapolation is greater than 20% may be excluded from descriptive statistics at the discretion of pharmacokineticist.

8.6.1.4 Anomalous Values

• If a value is considered to be anomalous due to being inconsistent with the expected pharmacokinetic profile, it may be appropriate to exclude this

point from the pharmacokinetic analysis. However, the exclusion of data must have strong justification and will be documented in the raw data and study report.

8.6.2 Presentation of Pharmacokinetic Data

8.6.2.1 **Presentation Pharmacokinetic Concentration Data**

- The following rules will be applied if there are values that are BLQ or if there are missing values (e.g., no result [NR]) in a concentration data series to be summarised.
 - For the calculation of summary statistics, BLQ values will be set to zero.
 - If an embedded BLQ value is considered anomalous within the concentration-time profile, this value will be excluded from the summary statistics.
 - Where there is NR, these will be set to missing.
 - If there are less than three values in the data series, only the min, max and N will be presented. The other summary statistics will be denoted as not calculated (NC). BLQ is considered a value.
 - If all the values are BLQ, then the arithmetic mean, arithmetic SD, median, min and max will be presented as zero, and the geometric mean and geometric CV% will be denoted as NC.
 - If the value of the arithmetic mean or median is below the lower limit of quantification, these values will be presented as zero and the geometric mean and geometric CV% will be denoted as NC.

8.7 Immunogenicity Analysis

All anti-drug antibody (ADA) data collected in eCRF will be listed for the ADA analysis set. Positive ADA status for a sample is defined as having the screen assay reported as detected and the confirmatory assay reported as confirmed. Negative ADA status for a sample is defined as either having an assay reported as negative or having the screen assay reported as detected and the confirmatory assays reported as not confirmed.

The number and percentage of subjects with positive or negative ADA status will be summarized by dose cohort for Part 1 or by treatment group for Part 2 and time point.

8.8 Safety

All safety analyses will be conducted for the Safety population.

8.8.1 Extent of Exposure

Exposure data for the study treatment will be listed for both Part 1 and Part 2.

For Part 2, the following variables will be summarized for each treatment group:

- Treatment duration: Treatment duration (days) is defined as the date of last infusion the date of first infusion +1.
- Number of infusions
- Cumulative dose: cumulative dose is defined as the sum of all doses taken during treatment period.
- Type of modification including drug interrupted, withdrawn, reduced, delayed/not given, or rate changed.

8.8.2 Adverse Events

All adverse events (AEs) recorded on the eCRF will be coded using the MedDRA dictionary [Version 22.0 (or a later version if updated during the study)] and classified as pre-treat AEs, or treatment-emergent AEs as follows:

- Pre-treat AEs are events that start prior to the date of first dose of study treatment;
- TEAEs are events with start date on or after the date of first dose of study treatment, or with a start date prior to the date of first dose of study treatment whose severity worsens on or after the date of first dose of study treatment. TEAEs will be limited to those events occurring within 28 days after the last injection of study treatment, with AEs occurring after that being defined as post-treatment. AEs with missing start date after applying imputation rules will be considered as TEAEs.

Assessment of AE severity will be based on the Common Terminology Criteria for Adverse Events (CTCAE, version 5.0). Missing severity will not be imputed.

The relationship between an AE and study treatment is assessed as definitely, probably, possibly, unlikely, or not related. A treatment-related AE is an AE considered by the investigator as definitely, possibly, or probably related to study treatment or with unknown/missing relationship to study treatment.

All AE data will be listed. Treatment-emergence status will be flagged in the listing. In addition, corresponding listings of serious AEs (SAEs), AEs leading to discontinuation from study, AEs of special interest, and AEs resulting in death will be produced. Summary tables of TEAEs by dose cohort for Part 1 or by treatment group for Part 2 and overall will be produced.

An overview table will summarize the number and percentage of subjects with at least one of the following TEAEs, where subjects with more than one TEAE in a particular category are counted only once in that category:

- Any TEAE;
- TEAE by maximum severity;
- Treatment-related TEAE;
- TEAE leading to discontinuation from study;
- TEAE of Special Interest;
- Serious TEAE;
- Treatment-related serious TEAE;
- Serious TEAE leading to discontinuation from study;
- Serious TEAE leading to death.

The number of total TEAEs will be also included in the overview table.

The number and percentage of subjects reporting each TEAE will be summarized by SOC and PT, or PT. Tables will be sorted in descending overall frequency by SOC, and then in descending overall frequency by PT within SOC, and then alphabetically. The following summaries will be produced:

- TEAEs, by SOC and PT;
- TEAEs, by PT;
- TEAEs, by SOC and PT and maximum severity;
- Treatment-related TEAEs, by SOC and PT;
- Lumbar Puncture procedure related TEAEs, by SOC and PT (Part 2 only);
- TEAEs leading to discontinuation from study, by SOC and PT;
- TEAEs of Special Interest, by SOC and PT;
- Serious TEAEs, by SOC and PT;
- Treatment-related serious TEAEs, by SOC and PT;
- Lumbar Puncture procedure related serious TEAEs, by SOC and PT (Part 2 only);
- Serious TEAEs leading to discontinuation from study, by SOC and PT;
- Serious TEAEs leading to death, by SOC and PT.

In the above summaries, subjects with more than one AE within a particular SOC are counted only once for that SOC. Similarly, subjects with more than one AE within a particular PT are counted only once for that PT. For summaries by maximum severity, subjects with multiple AEs within a particular SOC or PT will be counted under the category of their most severe AE within that SOC or PT.

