During the lumbar puncture, an amount of CSF approximately equivalent to the amount of investigational product to be injected into the intrathecal space (~9-20 mL) will be obtained predose for CSF/PK assessment, spinal cord injury biobanking, and potentially biomarker analysis. For the 20 mL maximum dose, at least 15 mL of CSF should be collected immediately prior to administration. If at least 15 mL cannot be collected, the principal investigator may elect to skip dosing for the visit or to ask the subject to return on the following day for a second attempt after additional hydration. In this situation, the subject may be directed to remain at a nearby overnight accommodation or home (if within a reasonable distance) and report the next morning for examination or to remain in the hospital overnight. Note that, under these circumstances, there is no requirement for an overnight hospital stay; if a decision is made to keep the patient overnight for convenience (e.g. travel issues), this hospitalization should not initiate a serious adverse event report (e.g. local alternate accommodations not readily available). Investigational product will be administered via slow bolus infusion intrathecal administration. Details including dose and quantity administered, physician administering the investigational product, and date and time of administration will be recorded on the eCRF and in the subject's record. Post lumbar puncture and post-dose subjects are to be monitored for any adverse events.

The Site Principal Investigator may discontinue a subject from the study due to unsuccessful collection of CSF to allow for isovolumetric dose administration if the subject has not received any doses and they consider it unlikely that further dosing attempts will be successful. Subjects who received at least one dose of investigational product should complete the remaining visits to monitor for safety and efficacy as per the schedule of events. Under this circumstance, further per-protocol LP attempts should not be made. Conducting all LPs under fluoroscopy should be considered if difficulties in obtaining adequate CSF collection is encountered.

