#### 11.2.4. Follow-up Visits 8 and 9 (Study Days 169 and 253)

At Visits 8 and 9 (Study Days 169 and 253), 12-Lead ECGs, physical examinations (abbreviated at Visit 8; full exam at Visit 9, with height/weight), vitals will be performed. Serum samples will be collected for PK and ADA analysis as detailed in Section 13.2. Blood will be collected for laboratory testing and viral serology, and urine collected for urinalysis. Urine pregnancy tests will be conducted for women of childbearing potential. Changes to concomitant medication will be assessed and recorded as well as AEs and SAEs. CSF will be collected at Visit 9 (Study Day 253).

In Study Visits 8 and 9, subjects will have all efficacy and QoL assessments performed (see the Schedule of Events for specifics, Table 6), in the following order:

- ISNCSCI
- GRASSP. Note: GRASSP prehension ability and prehension performance testing will be video recorded.
- Modified Ashworth Scale, fingers and thumb excluded
- SCIM III Self-Care & Mobility subscores
- Brief Pain Inventory
- Neuro-QOL Item Bank v1.0 Upper Extremity Function (Fine Motor, ADL)
- SF-36 v2 Health Survey
- CUE-Q
- PGIC Chronic SCI
- International Standards to document remaining Autonomic Function after Spinal Cord Injury (ISAFSCI)

GRASSP prehension ability and prehension performance testing will be video recorded.

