#### 14.2.5. Adverse Event Reporting

The investigator is to record all directly observed AEs and all AEs spontaneously reported by the subject in the source documents and eCRFs.

All observed or volunteered AEs regardless of treatment arm or suspected causal relationship to the investigational product(s) will be reported as described in the following sections.

For all AEs, the investigator must pursue and obtain information adequate both to determine the outcome of the AE and to assess whether it meets the criteria for classification as an SAE requiring immediate notification to the sponsor or its designated representative. For all AEs, sufficient information should be obtained by the investigator to determine the causality of the AE. The investigator is required to assess causality. For AEs with a causal relationship to the investigational product, follow-up by the investigator is required until the event or its sequelae resolve or stabilize at a level acceptable to the investigator, and the sponsor concurs with that assessment.

In order to ascertain if headaches are secondary to the lumbar puncture per se, the clinical characteristics of the headache, including positional exacerbations will be assessed and reported. For Part 1, adverse events should be recorded and monitored from the time of first dose through subject completion of the study up to 28 days post-dose, or until the investigator deems the AE as resolved or stable (unchanging). Serious AEs should be recorded and monitored from the time of signing of the informed consent form (ICF) through subject completion of the study up to 28 days after completion of the study, or until investigator deems the SAE as resolved or stable (unchanging).

For Part 2, adverse events should be recorded and monitored from the time of first dose up to 28 days after completion of the study (28 days after Month 9 visit or ET), or until the investigator deems the AE as resolved or stable (unchanging). Serious AEs should be recorded and monitored from the time of signing of the informed consent form (ICF) through subject completion of the study (28 days after Month 9 visit or ET), or until investigator deems the SAE as resolved or stable (unchanging).

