## 15.11. Safety Endpoints

The safety analysis will be descriptive in nature. All safety data will be listed, and data will be tabulated by dose (Part 1) and treatment group (Part 2) where the data warrant. Safety data include:

- AEs, including assessment of lumbar infusion site
  - Events occurring prior to the first dose of investigational product or placebo will be defined as pre-treatment events.

- For Part 1, TEAEs will be defined as any AE occurring during or after the injection of study drug. This will therefore include all events occurring through Day 29/ET.
- For Part 2, TEAEs will be limited to those events occurring within 28 days after the last visit.

Incidence of AEs will be summarized for each treatment group/cohort by MedDRA system organ class (SOC) and preferred term, sorted in descending frequency by SOC, and then by preferred term within SOC. These summaries will be given by treatment in separate tables for each of the following TEAE event sets:

- All events
- Treatment related events (defined by a relationship to study drug of possible, probable, or definite).
- Serious adverse events
- Events leading to premature discontinuation from study
- Events by maximum severity
- AEs of Special Interest, ie, events relating to the lumbar puncture procedure (eg, infection, headache, back pain, excessive CSF leakage requiring blood patch).

Other safety outcomes will include:

- Clinical laboratory tests, including hematology, chemistry, metabolic, and urinalysis. Changes over time will be presented. Potentially clinically significant (PCS) ranges will be defined and used to determine the incidence of subjects experiencing newonset PCS laboratory values, where new-onset is defined as a PCS value for a subject following initiation of study treatment for which the subject did NOT have a PCS value for that analyte PRIOR to initiation of study treatment.
- Vital signs including: respiratory rate or pulse oximetry, heart rate, temperature, and blood pressure, as per the schedule of events. BMI will be assessed, with height collected only at screening.
- Physical examination
- 12-lead ECG. ECG parameters will be analyzed in a fashion similar to that of clinical laboratory parameters.

Condition-specific safety outcomes will include:

- ISNCSCI, GRASSP and all of the neurological measures evaluated for efficacy

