8.9 Interim Analysis

No interim analysis will be performed for this study.

9. Changes from the Protocol Specified Statistical Analyses

The following changes from protocol specified statistical analyses are made in this SAP.

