9.3 Analysis population

PK Analysis set and ADA analysis set were added in the SAP for analysis for PK and ADA, respectively. In addition, mITT analysis set was added for Part 2 and all Part 2 efficacy analysis will be conducted using mITT analysis set.

10. Changes in the Planned Statistical Analyses

The following changes in the planned statistical analyses indicated below are being made after all enrolled Part 2 patients have completed the 6-month visit, cleaning and unblinding of data, and completion of the 6-month top-line analysis for the primary, secondary and exploratory efficacy endpoints to compare treatment effects from baseline to Study Day 169 and prior to final database lock following 9-month visit or Study Day 253 (as described in section 2.2). The availability of results of this analysis was limited to the unblinded ReNetX staff and **Compare** Biostatistics and Programming team. The changes were requested by the unblinded ReNetX staff after review of results and approved by **Compare** Biostatistics and Programming team.

10.1 Post Hoc Exploratory Analysis for Efficacy Endpoints to Study Day 169

Results from the primary efficacy analysis, based upon a mixed-effects model for repeated measures (MMRM) as described in section 8.5.2.1, showed that there was no statistically significant difference at the two-sided 5% significance level between AXER-204 and Placebo groups in the primary efficacy endpoint. Additionally, the MMRM subgroup exploratory analyses (as described in section 8.5.2.1.3) did not show statistical significant difference between treatment and control groups in the primary endpoint at the unadjusted two-sided 5% significance level, but there is visually a potential trend toward treatment effect in the subgroups AIS grade (B, C, D) and no prior receipt of study drug in Part 1.

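### The SAP ends the Part 2 TEAE window 28 days after the last injection, the protocol 28 days after the last visit; the change is undeclared and late adverse events enter no by-arm incidence table

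*SAP*

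**What the plan says.** **SAP 8.8.2.** The rule is "TEAEs will be limited to those events occurring within 28 days after the last injection of study treatment". Anything later is post-treatment. The overview table and every table by system organ class and preferred term are restricted to TEAEs. That includes the serious, fatal, special-interest and lumbar-puncture-related tables. Post-treatment events appear only in listings.

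**Protocol 15.11.** The rule written specifically for Part 2 is "For Part 2, TEAEs will be limited to those events occurring within 28 days after the last visit". Protocol 14.1 and the synopsis use the same last-visit anchor for both Parts.

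**Protocol 14.2.5.** For Part 2, "adverse events should be recorded and monitored from the time of first dose up to 28 days after completion of the study", and completion is spelled out there as the Month 9 visit or early termination. The collection period and the protocol's TEAE window therefore end together.

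**Follow-up after dosing stops.** Where cerebrospinal fluid cannot be collected, Protocol 11.2.2 says: "Subjects who received at least one dose of investigational product should complete the remaining visits to monitor for safety and efficacy". Protocol 15.4 and SAP 7.3.2 keep anyone who discontinues treatment in follow-up, where possible.

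**Record of changes.** SAP section 9 opens with "The following changes from protocol specified statistical analyses are made in this SAP" and then covers the PGIC endpoint, exploratory endpoints and analysis populations. Section 10 covers post hoc efficacy analyses and the slope model. Neither mentions the TEAE window.

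**The concern.** Comparing safety and tolerability with placebo is a primary objective of Part 2, and the two documents would produce different by-arm adverse event tables for it.

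The period left out is not an idle one. It contains the Day 169 and Day 253 safety visits and the lumbar puncture at Day 253; the Day 137 safety call also falls after the cut-off on the nominal schedule. Protocol 14.2.3 lists increased pain, increased spasticity and late-onset epidermoid tumours among the events of special interest, and refers to theoretical harms from axon growth. Protocol 13.1.2 treats change through Day 169 as the most relevant to on-target effects. Benefit is thus judged at Day 169, while the tabulation of harms stops 37 days earlier (169 − 132).

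The gap widens for a subject who stops dosing early, because follow-up continues while the SAP window closes 28 days after that subject's last dose. This would make the arms unequal only if early stopping differed between them. The documents give no expected rate, so no imbalance is assumed here.

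**Working it through.** **Inputs.** Doses are planned at Days 1, 21, 42, 63, 84 and 104 (±5 days after the first), and the last visit is Day 253 ±7 days (Protocol synopsis and Table 6). The SAP window ends at last dose + 28 days; the protocol window ends at last visit + 28 days.

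**The plan's own figures.** Follow-up after the last dose: (253 − 104)/7 = 21.3 weeks, against 21 weeks stated. Participation: 84 + 253 = 337 days, as stated.

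**Fully dosed subject, nominal days**

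- SAP window ends: 104 + 28 = Day 132.
- Protocol window ends: 253 + 28 = Day 281.
- Days in the protocol window but not the SAP window: 281 − 132 = 149, and 149/281 = 53.0%.
- Split: 253 − 132 = 121 days up to the last visit, and 281 − 253 = 28 days after it with no scheduled contact.
- Counting only to the last visit: 121/253 = 47.8%.

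**Visit windows.** The sixth dose can fall on Days 99 to 109 and the last visit on Days 246 to 260. The SAP cut-off then lies between Day 127 and Day 137, and the protocol cut-off between Day 274 and Day 288.

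- Smallest share: (274 − 137)/274 = 137/274 = 50.0%.
- Largest share: (288 − 127)/288 = 161/288 = 55.9%.

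**By number of doses, subject followed to Day 253**

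| Doses | Last dose day | SAP cut-off (last dose + 28) | Days outside (281 − cut-off) | Share of 281 |
|---|---|---|---|---|
| 6 | 104 | 132 | 149 | 53.0% |
| 5 | 84 | 112 | 169 | 60.1% |
| 4 | 63 | 91 | 190 | 67.6% |
| 3 | 42 | 70 | 211 | 75.1% |
| 2 | 21 | 49 | 232 | 82.6% |
| 1 | 1 | 29 | 252 | 89.7% |

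**Lumbar punctures.** Seven are scheduled: six at dosing visits and one at Day 253 (Protocol Table 6 and 11.2.4). The six dosing procedures fall inside the SAP window. The seventh falls 121 days after the cut-off, so an event it causes cannot enter the table of lumbar-puncture-related TEAEs.

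**Incomplete dates.** Under SAP 7.3.1 an onset with the day missing is usually set to the first of the month, so an event up to 31 − 1 = 30 days after the cut-off can still count. If day and month are both missing and the year is the year treatment started, the event is dated to the start of treatment and counts. A wholly missing start date also counts as treatment-emergent (SAP 8.8.2). The exclusion therefore applies to events whose onset is known.

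**Part 1, for comparison.** The SAP rule gives 1 + 28 = Day 29, nominally the same as the Day 29/ET end point in Protocol 15.11. Protocol 14.1 and the synopsis would give 29 + 28 = Day 57, although Protocol 14.2.5 stops Part 1 collection of non-serious events at 28 days post-dose. The practical effect is in Part 2.

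**The case against.** The strongest reply is that last dose + 28 days is a common and defensible window, and that the protocol is not clean enough to serve as a benchmark. If Part 2 events are collected to 28 days after the last visit, a TEAE limit at the same point excludes almost nothing. Table 6 also carries a Post-Trt label in the adverse event row, undefined for events, and Protocol 15.11 starts post-treatment medications 28 days after the last dose. On this reading the SAP may be repairing a drafting slip. That is possible, but no protocol text defines Part 2 TEAEs by last injection, and the SAP does not say it is resolving anything. Section 9 was the place to do so.

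Second, nothing is lost from the record. SAP 8.1 presents listings by treatment group, and 8.8.2 adds separate listings of serious events, special-interest events, events leading to discontinuation, and deaths. With about 32 subjects a reader could count late events by arm. A late death or withdrawal before Day 253 also appears as a discontinuation reason in the by-arm disposition table (SAP 8.2). Spasticity and pain are compared by arm at Days 169 and 253 (SAP 8.8.7), and laboratory, vital-sign and ECG data are summarised at later visits. All of this stands and limits the harm. A hand count from listings is still not the planned by-arm incidence table for a primary objective.

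Third, 53% leans high, because it includes 28 days without scheduled contact. SAP 2.2 also locks the database once all subjects have completed Day 253, with no stated wait, so those days may be incomplete for the last subjects enrolled. This is fair. The 121 days before the last visit are unaffected.

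**Conclusion.** The concern holds. The SAP and the protocol define the Part 2 TEAE window differently, the SAP does not declare the change, and an event with a known onset after the SAP cut-off enters no by-arm adverse event incidence table. For a fully dosed subject on schedule, 149 of 281 days fall outside (50% to 56% across visit windows), 121 of them before the last visit. The figure rises to 252 days for a subject given one dose and followed to Day 253.

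These are lengths of time; the documents do not allow an estimate of how many events are affected. The figures assume follow-up to Day 253 and that the protocol text read here is the version the SAP was written to (it cites V4.0). Safety analysis is descriptive, with no hypothesis test on adverse events, so no error rate is at stake. What changes is what the trial reports on its primary safety objective. This should be fixed, but it does not undermine the trial.

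**What to change.** - Keep last injection + 28 days as a set labelled on-treatment.
- Add by-arm Part 2 tables (system organ class and preferred term, serious, special-interest, lumbar-puncture-related, fatal) covering first dose to 28 days after the last visit. Equivalent by-arm post-treatment tables would also serve. Keep the SAP's rule for worsening of pre-existing events, so that the two sets differ only in end date.
- Declare the difference from Protocol 15.11 in the SAP. Section 10 records unblinding and "completion of the 6-month top-line analysis for the primary, secondary and exploratory efficacy endpoints", and SAP 2.2 plans all safety summaries at that same analysis. The added tables must therefore be marked as specified after unblinding and shown beside the existing set, not in its place.
- State whether the final lock waits 28 days after the last subject's Day 253 visit. If it does not, note that this stretch is incomplete.
- Reconcile the Part 1 and Part 2 windows across the protocol synopsis, 14.1 and 15.11, and define the Post-Trt label for adverse events in Table 6.

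The cost is SAP wording, one further set of tables and a protocol clarification. No data beyond those the protocol already collects are needed. The wider tables will include some background events remote from dosing, which is a reason to show both sets.

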### 6.2. Part 2 Placebo-Controlled Repeat Dose

#### 6.2.1. Primary Objectives

- 1. To evaluate the safety and tolerability of repeat intrathecal lumbar slow bolus infusions of AXER-204 compared to placebo in subjects with CSCI.
- 2. To evaluate the pharmacokinetics of repeat doses of AXER-204 in subjects with CSCI

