Exploratory functional endpoints will include within-subject changes from pre-treatment baseline and slope for:

• ISNCSCI lower extremity motor and sensory scores

- GRASSP strength, sensation and prehension ability scores
- SCIM III mobility scores
- Patient Reported Outcomes
  - CUE-Questionnaire (CUE-Q) [Marino 2012, Marino 2015]. Assesses subject-reported upper limb function (Appendix 2).
  - SF-36 v2 Provides an investigator-evaluated Quality of Life (QoL) assessment for subjects. SF-36 will provide data on the subjects' perceived health and wellbeing over the course of the study (Appendix 6).
  - Neuro-QOL Item Bank v1.0 Upper Extremity Function (Fine Motor, ADL) -(Appendix 7).
  - PGIC Chronic SCI (Appendix 10) Provides a patient-reported global impression of change in the symptoms, activity limitations, emotions and overall quality of life with chronic spinal cord injury since beginning the trial.
- ISAFSCI [Krassioukov 2012]. The ISAFSCI will be used to document autonomic control of the heart, blood pressure, sweating and temperature regulation. Lower urinary tract function, bowel function, and sexual function will be scored (Appendix 1).

Exploratory biomarkers of target engagement and axonal growth may be assessed.

Since the mechanism of action entails enhanced axonal growth and plasticity, changes attained through Study Day 169 are anticipated to be most relevant to assessing on-target effects of therapy.

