### 14.2.3. Adverse Events of Special Interest (AESI)

Adverse Events of Special Interest (AESI) for this study include possible allergic/immune reactions to administration of a protein therapeutic, AEs generally associated with lumbar puncture, and theoretical AEs arising from axon growth. No AESI have been identified from non-clinical toxicology studies with AXER-204. The following are considered AEs of Special Interest for this study:

- Immune/Allergic reactions: fever, rash, arthralgia, myalgia, hematuria, proteinuria, serositis, central nervous system complications, and hemolytic anemia. Injection site reactions may occur
- Events relating to the lumbar puncture procedure: infection, postdural puncture headache, bleeding, brainstem herniation, meningitis, back pain, excessive CSF leakage requiring blood patch
- Complicating infections: discitis and vertebral osteomyelitis
- Neurological symptoms or injuries: low back pain, radicular injury, abducens palsy
- Other: late onset of epidermoid tumors of the thecal sac, increased pain, increased spasticity

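### SAP 8.8.2 closes the Part 2 adverse-event tables 28 days after the last injection (about Day 132), where the protocol runs them to 28 days after the last visit (about Day 281), and Section 9 does not declare the change

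*SAP*

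**What the plan says.** The protocol gives the TEAE limit in three places: the Synopsis (Safety), Section 14.1 and Section 15.11. The last addresses the repeat-dose part directly: "For Part 2, TEAEs will be limited to those events occurring within 28 days after the last visit". Collection matches that definition. For Part 2, Section 14.2.5 states that "adverse events should be recorded and monitored from the time of first dose up to 28 days after completion of the study", and it counts those 28 days from the Month 9 or early-termination visit.

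SAP 8.8.2 gives one rule for both parts: "TEAEs will be limited to those events occurring within 28 days after the last injection of study treatment". Later events become post-treatment. The summaries that follow are all TEAE summaries: overall, by severity, treatment-related, lumbar-puncture-related, serious, fatal, leading to discontinuation, and "TEAEs of Special Interest, by SOC and PT". No table of post-treatment events is planned. All adverse events are listed with a treatment-emergence flag, and serious events, special-interest events, deaths and discontinuations also have their own listings.

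SAP Section 9, which records departures from the protocol, covers PGIC, exploratory endpoints and analysis sets. Section 10 covers post hoc subgroup analyses and the slope model. Neither mentions the TEAE window.

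**The concern.** The first primary objective of Part 2 is comparative: "To evaluate the safety and tolerability of repeat intrathecal lumbar slow bolus infusions of AXER-204 compared to placebo". It needs by-arm tables over the period in which events are collected. Under the SAP rule those tables stop well before follow-up ends.

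Three features of the design make the later period relevant.

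- The special-interest events in protocol 14.2.3 include some that need not appear early: "late onset of epidermoid tumors of the thecal sac, increased pain, increased spasticity".
- CSF is collected again at Day 253 (protocol Table 6 and 11.2.4), and complications of lumbar puncture are themselves special-interest events. The SAP plans Part 2 tables of lumbar-puncture-related TEAEs, but a new event after the Day 253 procedure could not enter them.
- The SAP window shortens with early cessation of dosing, while follow-up does not. Under protocol 11.2.2, subjects with at least one dose whose CSF collection later fails "should complete the remaining visits to monitor for safety and efficacy as per the schedule of events". Protocol 15.4 likewise continues follow-up, where possible, after treatment is stopped for any reason.

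**Working it through.** **Inputs.** Screening is up to 84 days. Doses are on Days 1, 21, 42, 63, 84 and 104, with ±5 days from Day 21 on. Follow-up visits are on Days 169 and 253 (±7), with a call on Day 137 (±7). All are from protocol Table 6 and Sections 7.1.2 and 10. Day 1 is the first dose (SAP 7.1).

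**The plan's own timeline.** Participation = 84 + 253 = 337 days, as stated. Treatment = 104/7 = 14.9 weeks (stated as 15). Follow-up = (253 − 104)/7 = 21.3 weeks (stated as 21). The day numbers are consistent.

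**Window ends, six doses and full follow-up.**

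- SAP: last injection + 28 = 104 + 28 = Day 132. With the ±5-day window: 99 + 28 = 127 to 109 + 28 = 137.
- Protocol: last visit + 28 = 253 + 28 = Day 281. With the ±7-day window: 246 + 28 = 274 to 260 + 28 = 288.
- Difference: 281 − 132 = 149 days, and 149/281 = 53%. Extremes: (274 − 137)/274 = 50% and (288 − 127)/288 = 56%.

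The 149 days are 121 from the cut-off to the Day 253 visit plus the 28 days after it. The nominal Day 137 call and both follow-up visits fall in this stretch. Classification is by onset date, so an event that began by Day 132 is counted even if first reported at one of those contacts.

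**Dosing stopped early, follow-up completed.**

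| Last dose | SAP window ends | Days to 281 outside the tables |
|---|---|---|
| Dose 1, Day 1 | Day 29 | 252 (90%) |
| Dose 2, Day 21 | Day 49 | 232 (83%) |
| Dose 3, Day 42 | Day 70 | 211 (75%) |

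These rows show how the rule behaves. The documents give no discontinuation rate, so they do not show how many subjects it would affect.

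**Part 1 for comparison.** With one dose on Day 1, the SAP rule gives 1 + 28 = Day 29. That is the last Part 1 visit and the end that protocol 15.11 names for Part 1. The SAP rule therefore fits Part 1 and departs from the protocol only in Part 2, where dosing and the last visit are far apart.

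**The case against.** **The protocol is not uniform.** Its Part 2 schedule labels adverse events in follow-up as post-treatment, and 15.11 starts post-treatment medications at 28 days after the last dose, the same boundary that the SAP uses for events. This stands as support for having a post-treatment category. It does not displace a TEAE definition stated three times, once specifically for Part 2, and it does not explain why the later category gets no table.

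**Late events are still reported.** A reader might infer that they are lost. They are not: they are collected and listed, and SAP 8.1 presents listings by treatment group. With about 16 subjects per arm a careful reader could count them. Laboratory, vital-sign and ECG data are also still summarised by visit and arm. What is missing is the by-arm tabulation of adverse events.

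**53% is calendar time.** A reader might take it as the share of events missed. The documents give no event rates, and the last 28 days contain no scheduled contact. All six dosing procedures, and 28 days after each, lie inside the SAP window.

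**No late harm is predicted.** Protocol 13.1.2 says that "changes attained through Study Day 169 are anticipated to be most relevant to assessing on-target effects of therapy". A reader might infer an expectation of harm after Day 132. The sentence is about efficacy, and the SAP window covers 132 of those 169 days.

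**Nothing shows a data-driven choice.** A reader might suspect that the window was shortened after results were seen. The documents do not say when the rule was written, and its fit to Part 1 suggests a single rule carried over to both parts.

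**Conclusion.** The point holds for the adverse-event window. For Part 2, SAP 8.8.2 departs from the protocol definition without declaring it. For a subject with six doses on schedule and a Day 253 visit, about 149 of 281 days of adverse-event follow-up (50% to 56% across visit windows) feed no by-arm table. The share is larger for subjects who stop dosing but stay in follow-up, and smaller for those who leave the study early. This affects reporting on a primary objective, leaves efficacy conclusions untouched, and should be corrected before the final analysis.

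A minor note concerns the Modified Ashworth Scale and the Brief Pain Inventory. SAP 3.2 and 8.8.7 class both as safety variables but give them the MMRM and slope analyses with p-values, while protocol 15.3 and 15.11 rule out inference on safety data. A reader might infer a flat breach. The documents do not support that. The protocol also lists ISNCSCI and GRASSP as condition-specific safety outcomes and yet tests them for efficacy, so the bar cannot be absolute for scales with two purposes. SAP 2.1.2.3 also places both scales among the exploratory efficacy objectives. What remains is a reclassification that Section 9.2 does not declare.

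**What to change.** In SAP 8.8.2, do one of two things for Part 2:

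1. Define TEAEs to 28 days after the last visit. If wanted, show an on-treatment subset to 28 days after the last injection.
2. Keep the present window, declare it in Section 9, and add by-arm n (%) tables of post-treatment adverse events, serious events and special-interest events by SOC and PT.

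Label either change in Section 10 as made after the Day 169 unblinding. SAP 2.2 has all safety summaries produced at that stage, and Section 10 confirms that sponsor staff had been unblinded. Restoring the protocol rule brings in no new definition, but the date of the change should still be visible.

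For the spasticity and pain scales, present the model differences with 95% confidence intervals as descriptive, or add a line to Section 9.2 declaring them exploratory efficacy endpoints.

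The cost is one cut-off or a small set of tables, plus a few lines of text. No new assessments are needed. The longer window brings more background events into both arms; the on-treatment subset keeps the period close to dosing visible.
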